**Sequences of Aerobic and Resistance Exercise and Cardio-metabolic Functions in T2D (ARRA)**

**NCT06145542**

**January 25, 2025**

**Study Protocol and Statistical Analysis Plan**

## **Participants**

Fifty-six T2D patients aged 50 years to 70 years, with a duration of T2D of at least one year. T2D is diagnosed by physicians according to the following criteria: random blood glucose  $\geq 11.1 \text{ mmol}\cdot\text{L}^{-1}$  (200 mg·dL $^{-1}$ ), fasting plasma glucose  $\geq 7.0 \text{ mmol}\cdot\text{L}^{-1}$  (126 mg·L $^{-1}$ ), oral glucose tolerance test  $\geq 11.1 \text{ mmol}\cdot\text{L}^{-1}$  (200 mg·dL $^{-1}$ ), or HbA1c  $\geq 6.5\%$  (48 mmol/mol).

Exclusion criteria are patients with T1D, diseases diagnosed by physicians that are unsuitable for exercise intervention, patients who have regular physical activity habits (90min moderate intensity exercise or 75min high intensity exercise), and currently under dietary program for weight loss.

## **Randomization**

Participants are randomized in a 1:1 ratio into aerobic-then-resistance exercise group (AR, n=28) and resistance-then-aerobic exercise group (RA, n=28). Randomization is stratified by age and HbA1c ( $\leq$  or  $>$ medians) with a block size of 4.

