## **Assessments of regular glycemic outcomes and covariates**

Baseline information included age, sex, duration of T2D, and medication are obtained by the specialist physician during the recruitment procedure. Prior to the exercise intervention, participants' body mass index (BMI) and blood pressure were measured at the study site. Measurements of participants' fasting plasma glucose, fasting insulin, and hemoglobin A1c (HbA1c) are taken within the week before and after an 8-week exercise intervention. Following an overnight fasting period of  $\geq 8$  hours, 10 ml of venous blood is collected before breakfast (7:00-8:00), and tested by the Laboratory Department of the Community Health Service Center.

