### **Statistical analysis plan**

A sample size of 54 participants is considered adequate to achieve 95% power for detecting within-between interactions, using measures taken at pre- and post-intervention time points, based on a medium effect size ( $f = 0.25$ , G\*Power, version 3.0.10). Analyses are carried out following the intention-to-treat principle. The personnel who conduct the analyses are blinded about participants' randomization group. Data are checked for normality by using the Shapiro-Wilk test. Between group comparisons of the outcome variables are

conducted using analysis of covariance (ANCOVA), controlling for the baseline value of the variable of interest, while within-group pre-post-intervention comparisons are performed using paired samples t-tests. Between-group comparisons of non-normally distributed outcome variables are conducted using the Mann-Whitney U test, and within-group comparisons are conducted using the Wilcoxon signed-rank test. Repeated measures analysis of variance (ANOVA) is used to analyze blood glucose levels at various time points during exercise and recovery periods (90 minutes post-exercise), including the main effects of time and group, as well as interaction between time  $\times$  group. Additionally, the change rates of overnight blood glucose levels recorded by CGM on non-exercise days are analyzed for the main effect of group. Between group comparisons of baseline values are analyzed using independent samples t-tests, Mann-Whitney U test, or chi-square test. All tests are two-tailed, P values  $< 0.05$  are considered statistically significant. All analyses are performed using SPSS statistical software version 26 (IBM Corp., Armonk, NY, USA).

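### Randomisation is stratified by age and HbA1c, but age enters no between-group model and HbA1c only its own ANCOVA, which costs some precision

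*Combined protocol and SAP*

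**What the plan says.** The Randomization section states "Randomization is stratified by age and HbA1c", with each factor cut at its median, "with a block size of 4", and equal arms of 28. That gives four strata for 56 patients.

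The Statistical analysis plan lists these between-group analyses:

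- ANCOVA, "controlling for the baseline value of the variable of interest".
- For skewed outcomes: "Between-group comparisons of non-normally distributed outcome variables are conducted using the Mann-Whitney U test".
- Repeated-measures ANOVA of glucose during exercise and recovery, with time, group and their interaction as the only terms.
- Overnight CGM: "change rates of overnight blood glucose levels recorded by CGM on non-exercise days are analyzed for the main effect of group". No covariate is named.

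The section headed "Assessments of regular glycemic outcomes and covariates" includes age among the baseline data, but no analysis takes it up.

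**The concern.** Stratified blocks nearly equalise the arms on age group and HbA1c group, so the group difference varies less from trial to trial than under simple randomisation. A model that omits the factors leaves their variation in the residual, and so reports a standard error that is too large. The test then rejects less often than its nominal 5% under the null, and power is lost.

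This is a question of efficiency, not of validity. The size of the loss depends on how much age and HbA1c predict an outcome after its own baseline is in the model. The sharpest case is HbA1c itself. If the normality check sends it to Mann-Whitney, the analysis drops a variable that is both a stratification factor and the outcome's own baseline.

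**Working it through.** **Inputs from the documents.** N = 56, 1:1, blocks of 4 in 2 × 2 median strata; two-sided α = 0.05; the plan's sample size of 54 for 95% power at f = 0.25.

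**Assumed, because the documents do not say.** Pre-post correlation ρ = 0.5; R², the share of outcome variance left after own-baseline adjustment that age and HbA1c explain, from 0 to 0.20; skewed outcomes generated as exp(0.8y); Mann-Whitney applied to post-intervention values.

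**1. The plan's own figure.** For the group-by-time interaction with m = 2 time points, λ = N·m·f²/(1 − ρ) = 54 × 2 × 0.0625 / 0.5 = 13.5. On F(1, 52) this gives power 0.950, so the stated figure reproduces at ρ = 0.5. As a two-group comparison of changes, λ = N·d²/4, so d² = 4 × 13.5 / 54 = 1.0. The planned effect is therefore 1.0 SD.

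**2. Approximate type I error without the factors.** If stratification removes a share s of the residual variance from the group contrast but the model still counts it, the effective critical value is t/√(1 − s). For a normal predictor cut at its median, the strata capture 2/π = 0.637 of its variance, so s ≈ 0.637·R². With t = 2.006 on 53 df:

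- R² = 0.10: 2.006/√0.936 = 2.073, type I error 0.043.
- R² = 0.20: 2.006/√0.873 = 2.147, type I error 0.036.

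**3. Simulation, ANCOVA, outcomes other than HbA1c** (10,000 trials per null cell, 6,000 per power cell; age and HbA1c continuous). The arrows run from own baseline only to own baseline plus age and HbA1c.

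| R² | Type I error, own baseline only | Change in mean SE when factors are added | Power at 0.5 SD | Power at 0.67 SD |
|---|---|---|---|---|
| 0 | 0.048 | +1% | 0.56 → 0.55 | 0.80 → 0.79 |
| 0.05 | 0.047 | −2% | 0.55 → 0.56 | 0.80 → 0.82 |
| 0.10 | 0.044 | −4% | 0.57 → 0.60 | 0.81 → 0.84 |
| 0.20 | 0.036 | −10% | 0.55 → 0.64 | 0.81 → 0.87 |

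With the factors in the model, type I error is 0.048–0.050. At 1.0 SD, power is about 0.99 either way. For HbA1c as the outcome with age added, power at 0.67 SD goes from 0.81 to 0.83 (R² 0.05) and from 0.81 to 0.84 (R² 0.10).

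If the factors act as two-level predictors at the strata cuts, s equals the full share and the ANCOVA is more conservative: 3.9% and 3.2% at shares of 10% and 20%.

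**4. Mann-Whitney, skewed HbA1c.** Baseline HbA1c explains ρ² = 0.25 of the post value on the unskewed scale, so s ≈ 0.637 × 0.25 = 0.159. Then 1.96/√0.841 = 2.137, a type I error of about 0.033. Simulation gives 0.030–0.032 for R² 0–0.10. Power at 0.67 SD is 0.68, against 0.78–0.81 for ANCOVA on ranks with baseline HbA1c and age.

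**5. Mann-Whitney, other skewed outcomes.** Power at 0.67 SD is 0.65–0.67, against 0.77–0.79 with ranked ANCOVA. Nearly all of that comes from the outcome's own baseline; age and HbA1c add 0–2 points.

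**6. Repeated-measures ANOVA** (two-time-point version, two-level factors). The group main effect has type I error of 4.2% and 3.0% at shares of 10% and 20%. The interaction stays at 4.9%–5.2% when the factors shift all time points equally. The overnight CGM test was not simulated; the same mechanism applies to it.

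**The case against.** The strongest reply is that little is lost. The planned ANCOVA is valid. At the only effect size in the documents the gain is under one point, and the larger gains appear at 0.5 and 0.67 SD, which are illustrative choices.

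R² may also be near the low end. Age is restricted to 50–70 years, and the own baseline of a glycaemic outcome may already carry most of what HbA1c predicts. In an illustrative case with baseline glucose correlated 0.7 with HbA1c and no direct HbA1c effect, type I error was 5.1%, so nothing was lost. This stands, and it limits the ANCOVA point to a modest one.

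The large Mann-Whitney gap for HbA1c comes mostly from dropping the own baseline. Ranked ANCOVA with that baseline alone reaches 0.77–0.79, and age adds 0–3 points. This also stands. For HbA1c, however, the own baseline is a stratification factor, so the conservatism there is a direct result of leaving a factor out.

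The plan does not say whether Mann-Whitney compares post values or changes. At a correlation of 0.5 this makes no difference. At 0.7 it does: type I error for HbA1c is 0.013–0.020 on post values but 0.034–0.044 on changes, and power at 0.67 SD is 0.68–0.72 against about 0.87. The Mann-Whitney figures should be read with that in mind.

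None of this supplies the missing covariates or gives a reason for leaving them out.

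**Conclusion.** The concern holds as an efficiency point. The design stratifies on two variables that the analysis then almost wholly ignores.

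In the ANCOVA the cost is small: about 2–3 power points at 0.67 SD for R² of 0.05–0.10, 6 points at R² of 0.20, and under one point at the planned 1.0 SD. It is larger if HbA1c is skewed, at 10–13 points at 0.67 SD, most of which is the lost own baseline.

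These sizes rest on assumed values of R², the pre-post correlation and the skew, and on Mann-Whitney being applied to post values. Results are not biased and false positives are not inflated. The sample size need not change.

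**What to change.** In the Statistical analysis plan:

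- Name baseline age and baseline HbA1c as covariates in every between-group ANCOVA, alongside the outcome's own baseline. When HbA1c is the outcome, add age only.
- Include the same two covariates in the group main-effect tests for the overnight CGM change rates and the exercise-period glucose levels.
- Where Mann-Whitney is planned, use ANCOVA on ranked values with the ranked own baseline, age and HbA1c as covariates.
- Leave the time-by-group test as it is. It is a within-patient contrast, affected only if age or HbA1c changes the time profile.

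The cost is one or two sentences and one or two model degrees of freedom. Both variables are already collected. If neither factor proves prognostic, the loss is about one power point at 0.5–0.67 SD.

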## **Exercises intervention program**

Exercise intervention is implemented in the gym room at the Community Health Service Center. The room was equipped with multiple devices for both aerobic and resistance training, which allowed a maximum of six participants to perform exercise at the same time. Room temperature is between 18-22 °C, controlled

by air conditioning. The training program is designed to take place three times a week for a total of eight weeks. Exercise intervention is scheduled for approximately 70 minutes per session (30 minutes of aerobic and 30 minutes of resistance, no break between two types, 5-min of preparation and 5-min relaxation stretching movements before and after each intervention), performed between 8:00 to 11:00 or between 14:00 to 16:30, Monday through Saturday. Exercise sessions starts at least 30 minutes after meals.

The target heart rate during aerobic exercise is set as resting heart rate (HR) + 40%-70% of heart rate reserve (HRR). Participants' HRR was calculated based on their resting HR and maximum heart rate ( $HR_{max}=208-0.7\times age$ ) as  $HR_{max} - HR$ . Heart rate monitors (OH1, Polar Oy, Oulu, Finland) are used during all exercise sessions to track exercise intensity and ensure that it remained within the specified range. Aerobic exercise is performed on bicycle ergometers (Ergoselect 100K, Ergoline GmbH, Bitz, Germany) for a continuous 30 minutes with a progressive intensity of 40%-70% HRR. Resistance level is set according to an adaptive training prior to the first intervention, pedal cadences are 50-60r/min.

Resistance exercise is conducted using a set of equipment (Nanjing Kuanyue Health Technology Co., Ltd, Nanjing, China) including chest press/ row, leg extension/ curl, abdominal/ back, biceps/ triceps, inner/ outer thigh, and push/ pull machines. Prior to conducting the 1 repetition maximum (RM) testing for the major muscles of the upper and lower limbs, all participants receive proper instructions on how to use the equipment. The Brzycki 1-RM prediction equation is used to estimate the 1RM based on the recorded resistance and repetitions. All participants performed resistance exercise with a weight of 60%-80% 1RM. Movements on each machine are repeated 10-12 times per unit for a total of 4 units, with a 30 second break between units. Resistance training involves progressive overload over an 8-week period.

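### A single stated block size of 4 makes about three in ten allocations certain to anyone tracking a stratum, if participants are randomised in stages

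*Combined protocol and SAP*

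**What the plan says.** All references are to the combined protocol and SAP.

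- **Randomization.** Allocation is 1:1, 28 per arm. "Randomization is stratified by age and HbA1c", each cut at its median, which gives four strata, "with a block size of 4". No second block size is mentioned. The section does not say where the medians come from, whether people are allocated together or as they enrol, or who holds the list.
- **Exercises intervention program.** Training takes place in one gym room at one community centre. The room "allowed a maximum of six participants to perform exercise at the same time", in sessions of about 70 minutes, three a week, "performed between 8:00 to 11:00 or between 14:00 to 16:30, Monday through Saturday". The arms differ only in which type of exercise comes first, so anyone in the room can see the allocation.
- **Assessments of regular glycemic outcomes and covariates.** HbA1c is not among the items collected at recruitment. Together with fasting glucose and insulin, its measurements "are taken within the week before and after an 8-week exercise intervention".
- **Statistical analysis plan.** Blinding is described for the analysts only.

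**The concern.** A fixed block of 4 in a 1:1 trial always closes with two participants in each arm. Anyone who knows the size and has seen the earlier allocations in the block knows the last one for certain, and sometimes the last two. Here the size is printed in the protocol and the allocations are visible on the gym floor. If new participants are still being enrolled, a recruiter who expects a particular order could hurry, delay or discourage a particular patient. Such selection can bias the comparison through characteristics that are not measured, and adjusting for the baseline value of the outcome would not remove it.

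This matters only if entry is staged. The plan does not say so, but two features point that way: the only baseline HbA1c described is taken shortly before training, and on its literal timetable the gym cannot train all 56 at once.

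**Working it through.** **Inputs.** Block size 4, four strata, 56 participants, 1:1 (Randomization; Participants). Six gym places, 70-minute sessions, windows of 180 and 150 minutes, six days a week, three sessions each (Exercises intervention program). The plan gives no figure for predictability, so there is none to reproduce.

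**1. Is staged entry plausible?** Sessions per place per day: floor(180/70) + floor(150/70) = 2 + 2 = 4. Places per week: 4 × 6 × 6 = 144. Needed: 56 × 3 = 168. So 144/3 = 48 participants can train concurrently.

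Two other readings remove the shortfall:
- If only the 60 minutes of aerobic and resistance work occupy a place: 3 + 2 = 5 slots, 5 × 36 = 180 places, 60 participants.
- If the windows are start times: 3 + 3 = 6 slots, 6 × 36 = 216 places, 72 participants.

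**2. Certain allocations, fixed block of 4.** The fourth allocation is always certain. The third is certain when the first two match, with probability 1/3. Per block: 1 + 1/3 = 4/3, and (4/3)/4 = 33.3%.

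With 56/4 = 14 per stratum on average, there are three full blocks and two left over. Certain allocations are 3 × 4/3 = 4, and 4/14 = 28.6%. Hence about 29–33%, or 56 × 0.286 = 16 to 56 × 0.333 = 18.7 participants.

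**3. Best-guess rate, fixed block of 4.** By position in the block: 1/2, 2/3, (1/3 × 1 + 2/3 × 1/2) = 2/3, and 1. These sum to 2.833, and 2.833/4 = 70.8%. For a stratum of 14: (3 × 2.833 + 1/2 + 2/3)/14 = 9.667/14 = 69.0%. Pure chance is 50%.

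**4. Mixed block sizes.** Take sizes 4 and 6 with equal probability and suppose a stratum opens A, A. Under a fixed block of 4, B is now certain. Under mixing:
- P(AA | 4) = 2/4 × 1/3 = 1/6, and P(AA | 6) = 3/6 × 2/5 = 1/5.
- P(size 6 | AA) = (1/5)/(1/6 + 1/5) = 6/11.
- P(next is A) = 6/11 × 1/4 = 3/22 = 14%.

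B is still the better guess, at 86%, but it is no longer certain. Simulating an observer who knows the possible sizes but not the order in which they occur gives about 3–10% certain allocations, depending on the mix. That is 1.7 to 5.6 of 56. The best-guess rate is about 68–72%, against 69% for the fixed block.

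**5. Cost in arm sizes.** Fixed blocks of 4 in four strata do not guarantee 28/28 either: simulation gives exactly 28/28 in about 43–53% of runs, with a largest difference of 8 (32/24). Relative efficiency at 32/24 is 4 × 32 × 24/56² = 0.980, and 0.980 × 56 = 54.9, still above the planned 54. (The plan's 54 for 95% power reproduces: power is 0.950 if a pre-post correlation of 0.5 is assumed, since the documents give none.)

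**6. Do moving medians harm balance?** Simulations assumed uniform ages from 50 to 70 and a skewed HbA1c. Running medians place about 14% of participants in a different stratum from the final medians. The SD of the standardised between-arm difference in baseline HbA1c is 0.191–0.197 with running medians, 0.185–0.193 with final medians and 0.27 without stratification. Cut-points fixed in advance (age 60, HbA1c 7.5% in the simulation) also differ from the final-median strata for about 10% of participants. Balance is nearly unaffected.

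**The case against.** The strongest reply is that nothing in the documents establishes sequential allocation. Gym capacity limits when people train, not when they are randomised. The shortfall vanishes under two other readings of the timetable. The stratifying HbA1c need not be the outcome measurement: participants have had diabetes for at least a year, so earlier values may exist. If all 56, or each whole cohort, are allocated as a batch, nobody in the batch is enrolled after seeing other allocations in it. Exploiting the block also requires knowing each candidate's stratum and past allocations, and the plan does not say that recruiters have either. All of this stands, and it makes the point conditional. It does not remove it, because the plan does not commit to batch allocation or to a concealed list.

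A reader might go further and infer that the strata cannot balance the arms, because a sample median is unknown until everyone is measured. The documents do not support that. They say only medians, without calling them sample medians, and step 6 shows that even running medians keep nearly all the gain. Reclassified participants lie near the cut, where it matters least, and the planned ANCOVA adjusts for the baseline outcome value, although not for age or where the Mann-Whitney test is used.

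Nor does it follow that the scheme works only if all 56 are randomised at once: preset cut-points and a concealed list would work with staged entry.

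**Conclusion.** The point holds in conditional form. If entry is staged, the single block size of 4 makes about 29–33% of allocations certain to a person who knows the size and tracks the stratum. Undisclosed mixed sizes would reduce this to about 3–10%. If allocation is by batch, the figure does not apply within a batch.

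The conclusion rests on three assumptions that the documents neither state nor exclude: staged entry, a recruiter who can learn earlier allocations, and knowledge of which stratum a candidate falls in. The risk is selective enrolment; power is not materially affected. The missing source and timing of the medians is a gap in reporting, not a fault in the balance of the design.

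**What to change.** In the Randomization section, replace the single block size with randomly mixed sizes, for example 4 and 6, or 2, 4 and 6. State that the sizes are not disclosed to staff who recruit or train participants, and keep them out of any document those staff hold. Because mixing removes certainty but leaves the average best-guess rate at about 68–72%, also state who holds the list and how each allocation is released.

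As a clarification, add the cut-point values or the source of the medians, which HbA1c measurement is used, and whether allocation is individual, by cohort or all at once.

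The cost is a change of wording and a regenerated list. Arm sizes may differ by a few participants, with trivial power loss. If allocation has already begun, the change can cover only those not yet allocated; if it is complete, report how the list was concealed and whether entry was staged.

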## **Continuous glucose monitoring**

Participants undergo a 14-day continuous glucose monitoring (CGM, FreeStyle libre Pro, Abbott Diabetes Care Ltd, Witney, UK) started at two time points: one week before initializing the exercise intervention and at the 8th week of the intervention. An ambulatory glucose monitoring sensor is attached to the posterior aspect of the participants' non-dominant arm, with a guide needle implanted into the subcutaneous tissues. Sensor attachment is manipulated by a research assistant at the study site, between 8:00 to 10:30 on the same day of blood sample collection. Participants do not have access to their own CGM data during the monitoring periods. Following the monitoring period, data are exported and saved from the sensor using scanner of the CGM system by a research assistant at the study site. CGM data collected starting from 00:00 on the second day following the sensor attachment until 00:00 on the day of sensor detachment are included in the analyses.

## **Assessments of regular glycemic outcomes and covariates**

Baseline information included age, sex, duration of T2D, and medication are obtained by the specialist physician during the recruitment procedure. Prior to the exercise intervention, participants' body mass index (BMI) and blood pressure were measured at the study site. Measurements of participants' fasting plasma glucose, fasting insulin, and hemoglobin A1c (HbA1c) are taken within the week before and after an 8-week exercise intervention. Following an overnight fasting period of  $\geq 8$  hours, 10 ml of venous blood is collected before breakfast (7:00-8:00), and tested by the Laboratory Department of the Community Health Service Center.

